4.3 Exclusion Criteria

1. Prostate cancer with known significant sarcomatoid, or spindle cell, or neuroendocrine small cell components, or metastasis of other cancer to the prostate
2. ⁶⁸Ga-PSMA PET/CT SUVmax < 10 at a site of measurable disease > 10mm
3. Prior treatment with enzalutamide, darolutamide, or apalutamide. Prior treatment with abiraterone is allowed.
4. Prior treatment with any PSMA-targeted radiotherapy
5. Prior chemotherapy for mCRPC. Prior docetaxel in castration-sensitive setting is permitted
6. History of another malignancy within 5 years prior to randomisation except for non-melanomatous carcinoma of the skin; or, adequately treated, non-muscle-invasive urothelial carcinoma of the bladder (i.e. Tis, Ta and low grade T1 tumours)
7. Concurrent illness, including severe infection that may jeopardise the ability of the participant to undergo the procedures outlined in this protocol with reasonable safety
8. Presence of any psychological, familial, sociological or geographical condition potentially hampering compliance with the study protocol and follow-up schedule, including alcohol dependence or drug abuse
9. Men in sexual relationships with women of reproductive potential who are not willing/able to use medically acceptable forms of barrier contraception

10. History of:

- a. seizure or any condition that may predispose to seizure (e.g. prior cortical stroke or significant brain trauma)
- b. loss of consciousness or transient ischemic attack within 12 months of randomization
- c. significant cardiovascular disease within the last 3 months:
including myocardial infarction, unstable angina, congestive heart failure (NYHA grade II or greater, see Appendix 4), ongoing arrhythmias of Grade > 2 (NCI CTCAE, version 4.03) , thromboembolic events (e.g. deep vein thrombosis, pulmonary embolism). Chronic stable atrial fibrillation on stable anticoagulant therapy is allowed

4.4 Study Enrolment

4.4.1 Pre-Screening

Written informed consent must be signed and dated by the participant, and signed and dated by the Investigator, prior to any study-specific screening investigations being performed.

4.4.2 Registration for ^{68}Ga -PSMA PET/CT

For registration to this study, potential participants must meet all of the eligibility criteria except those relating to imaging with ^{68}Ga -PSMA PET/CT (inclusion 6 and exclusion 2).

After participants are registered for the study, imaging with ^{68}Ga -PSMA PET/CT and FDG PET/CT will be performed. These procedures including manufacture of ^{68}Ga -PSMA are according to the Imaging Manual. The images will be completed at participating sites, and sent electronically in DICOM format to a central repository. The images will be centrally reviewed within 3 working days to determine eligibility for randomisation. Reason(s) for ineligibility will be recorded.

Participants who have provided consent but do not meet all the eligibility criteria will be recorded as screen failures.

4.4.3 Randomisation

Participants must continue to meet all of the inclusion criteria and none of the exclusion criteria to be randomised in this study. Participants will be randomly allocated (1:1) to treatment with either enzalutamide, or Lu-PSMA and enzalutamide.

If screening bloods were collected within 7 days prior to randomisation, baseline bloods do not need to be repeated.

Enzalutamide should be planned to start within 7 days after randomisation and Lu-PSMA within 21 days after randomisation. Randomisation will be done according to the instructions in the Study Manual. Once the randomisation process has been completed, the participant will be assigned a treatment group. Confirmation of each randomisation will be provided to the site. Individuals may only be randomised once in this trial.

5 TREATMENT PLAN

The experimental intervention in this trial is the combination of enzalutamide plus Lu-PSMA whilst the parallel arm is enzalutamide alone.

Participants in both groups are treated with a LHRHA (or surgical castration), as per standard of care. Androgen deprivation is to be given continuously in this trial. Intermittent androgen deprivation will be classified as a protocol violation. The dosing schedule for each treatment group is described in Table 1.

Table 1: Study Treatments

Agent(s)	Dose	Route	Duration
Enzalutamide	160 mg (four 40 mg capsules)	Orally	Daily until participant is no longer clinically benefiting, or experiences unacceptable toxicity
Lu-PSMA and Enzalutamide	7.5 GBq 160 mg (four 40 mg capsules)	IV Orally	All participants receive Lu-PSMA doses 1 and 2 (Days 15 and 57) unless unacceptable toxicity per section 5.2 of protocol. Doses 3 and 4 (Days 113 and 169) will be given following result of ⁶⁸ Ga-PSMA PET/CT at Day 92. Daily until participant is no longer clinically benefiting, or experiences unacceptable toxicity

5.1 Study Treatment

5.1.1 Lu-PSMA

The administered activity of Lu-PSMA is standardised at 7.5 GBq ($\pm 10\%$) for each treatment dose.

All participants on the experimental arm will receive 2 doses of Lu-PSMA on Days 15 (± 7) and 57 (± 7) unless there is unacceptable toxicity (See section 5.2). The first dose is administered 14 days (± 7 days) after starting enzalutamide.

Participants will undergo a repeat ⁶⁸Ga-PSMA PET/CT at Day 92 (± 7 days). ⁶⁸Ga-PSMA PET/CT at Day 92 allows sufficient time for central imaging review prior to determining a participant's suitability for further doses of Lu-PSMA. This scan should be performed no later than Day 99 (minimum 14 days before Day 113 Lu-PSMA treatment) to ensure adequate time is available for Lu-PSMA order and delivery.

Day 92 ⁶⁸Ga-PSMA PET/CT scans will be reviewed centrally. Participants will proceed with doses 3 and 4 at Days 113 (± 7) and 169 (± 7) if volume and intensity of residual PSMA avid disease is deemed adequate for target Lu-PSMA therapy on this scan, and if clinically appropriate (including meeting all safety criteria). Treatment will be administered to a maximum of 4 cycles, at a minimum interval of 6 weeks (42 days), subject to availability.

Lu-177 is required to be ordered at least 10 days before the planned administration for each cycle.

Lu-PSMA will be administered by slow intravenous injection. SPECT/CT imaging encompassing the neck, chest, abdomen and pelvis will be performed 24 hours (\pm 4 hours) after Lu-PSMA administration. See Nuclear Medicine Manual for Lu-PSMA manufacturing, quality control, and administration details.

5.1.2 Enzalutamide (XTANDI® Astellas)

Enzalutamide is provided as 40 mg soft gelatine capsules administered as 160 mg (4 capsules) orally once daily until clinical disease progression, prohibitive toxicity or participant is no longer clinically benefiting.

Enzalutamide will be commenced within 7 days of randomisation.

Enzalutamide's potency is increased with the co-administration of strong CYP2C8 inhibitors e.g. gemfibrozil. In this trial, it is preferable that these medications are ceased prior to commencing enzalutamide. However if it is not possible for these medications to be ceased then participants will need to commence enzalutamide at 80 mg daily. These participants will not be permitted to have their dose of enzalutamide increased to 160 mg until they have ceased the co-administration of the strong CYP2C8 inhibitor.

5.1.3 Required Background Treatment

All participants are to receive ongoing background androgen deprivation therapy with a LHRH analog (LHRH agonist or antagonist) or surgical castration, as per standard of care. The choice of the LHRHA or surgical castration is at the discretion of the treating clinician.

Administration of the LHRHA should be according to the product information guide. Options include but are not restricted to: goserelin, leuprorelin, triptorelin, or degarelix.

5.2 Dose Modifications and Delays for Lu-PSMA

5.2.1 Reduction of Administered Activity of Lu-PSMA for Adverse Events

The next planned dose of Lu-PSMA will be reduced by 20% for participants who have a dose limiting toxicity in the preceding cycle. A single dose reduction is allowed. No additional dose reductions are permitted in subsequent cycles.

Dose limiting toxicities are defined as those considered both attributable to Lu-PSMA and dose-related (frequency and/or severity are related to the dose administered).

Dose-limiting toxicities for Lu-PSMA in this trial are defined as any one the following:

- nadir platelet count $<100 \times 10^9/L$
- nadir neutrophil count $<1.0 \times 10^9/L$
- dry mouth of Grade 2 (moderate symptoms; oral intake alterations [e.g., copious water, other lubricants, diet limited to purees and/or soft, moist foods]) or worse
- dry eyes of Grade 2 (symptomatic; multiple agents indicated; limiting instrumental ADL) or worse

- other significant dose-related toxicities, i.e. adverse events of Grade 3 or worse that are considered both attributable to Lu-PSMA and dose related. The need for dose reductions and delays for these 'other toxicities' should be first discussed with the study team.

There are no re-escalations of Lu-PSMA in this trial. If in doubt, please contact the study team.

5.2.2 Dose Delays for Lu-PSMA

If the platelet count is $<150 \times 10^9/L$ after Lu-PSMA administration, then the platelet count should be re-checked one week later. If the platelet count is declining and less than $100 \times 10^9/L$, the next dose of Lu-PSMA therapy will be deferred and bloods will be checked weekly. The next dose of Lu-PSMA should only be ordered when the platelet count is both rising and above $75 \times 10^9/L$. Administration of the next dose can proceed if pre-treatment bloods show platelets $>75 \times 10^9/L$.

Treatment should generally be withheld during AEs of severity Grade 3-4 (according to CTCAE v5.0), and not restarted until the adverse event has resolved to Grade 0-2. If in doubt, please contact the study team.

For AEs related to solely laboratory tests, the tests should be performed at least weekly to assess for recovery. The next dose of Lu-PSMA should not be ordered until the laboratory AEs have resolved to Grade 0-2. Blood transfusion to correct anaemia is allowed in this trial.

5.3 Dose Modifications for Enzalutamide

Participants who experience a Grade 3 or higher toxicity that is attributed to enzalutamide and cannot be ameliorated by the use of adequate medical intervention may interrupt treatment with study drug. Subsequently, study drug dosing may be restarted at the original dose (160 mg/day) or at a reduced dose (120 or 80 mg/day). Treatment interruption and re-initiation should be discussed with the study chair or delegate.

The dose of enzalutamide can be reduced to 120 mg/day for chronic long term Grade 2 adverse events (including but not limited to fatigue or cognitive impairment) at the site investigator's discretion. The dose reduction and justification must be documented in the participant's notes. Dose modifications for other scenarios may be considered for the wellbeing of the participant, with the approval of the study chair or delegate and documentation in the medical record.

If enzalutamide is co-administered with a **strong** CYP2C8 inhibitor (e.g. gemfibrozil), then the dose of enzalutamide should be reduced to 80 mg once daily. If co-administration of the **strong** CYP2C8 inhibitor is discontinued, then the enzalutamide dose should return to the dose used prior to initiation of the strong CYP2C8 inhibitor. See also sections 5.5.3 and 5.5.4.

5.4 Post-Study Treatment

Treatment after completion or discontinuation of study treatment is at the discretion of the patient's treating clinicians. Information on treatment administered post-study treatment will be collected for analysis as it may impact on longer-term outcomes (e.g. overall survival).

5.5 Concomitant Medications/ Treatments

5.5.1 Recommended

The following medications are recommended with Lu-PSMA treatment:

- Dexamethasone 8 mg orally on the day of Lu-PSMA injection at least 15 minutes prior to Lu-PSMA, and 4 mg on Day 2 and 3 after each Lu-PSMA dose.
- Metoclopramide should be provided as a take home medication to be used as required for nausea or vomiting.
- Other anti-emetics should be used as required as per standard clinical practice.

Anti-emetics for delayed nausea after Lu-PSMA treatment:

Delayed nausea after Lu-PSMA is common, and is thought to be radiation duodenitis rather than via a central mechanism.

Recommended management is prednisolone 5-10mg mane for two weeks, plus travacalm (dimenhydrinate, hyoscine, caffeine) one tablet as required 2-3 times daily, or metoclopramide 10mg as required 2-3 times daily.

Enzalutamide is associated with QTc prolongation and the following anti-emetics should be avoided because of their risk of QTc prolongation:

- 5-HT3 receptor antagonists such as ondansetron, granisetron and dolasetron
- Butyrophenones such as droperidol and haloperidol
- Phenothiazines such as chlorpromazine
- Domperidone

The following are recommended for osteoporosis treatment or prevention, associated with enzalutamide and LHRHA use:

- Calcium and/or vitamin D supplementation.
- Bisphosphonates or RANK-ligand inhibitors at doses relevant for the treatment or prevention of osteoporosis (e.g. zoledronic acid 5 mg every 12 months, or denosumab 60 mg every 6 months). Bisphosphonates or RANK-ligand inhibitors given for purposes of preventing skeletal-related events (e.g. denosumab 120 mg every 4 weeks) should be initiated within 2 weeks of commencing study treatment.

5.5.2 Permitted

Palliative radiotherapy to pre-existing metastases is permitted without the requirement for withdrawal from study treatment, as long as the investigator deems the participant continues to derive clinical benefit from continued study treatment. Requirement for radiotherapy to new metastases indicates clinical progression of disease.

5.5.3 Use with Caution

Some drugs affect the metabolism of enzalutamide. Enzalutamide is metabolised by the liver and the cytochrome P450 pathways 2C8 and 3A4 are responsible for the metabolism of enzalutamide. Interactions between enzalutamide and other drugs (e.g. trimethoprim, gemfibrozil, rifampicin, and itraconazole) which inhibit or induce CYP2C8 and CYP3A4 can occur and caution is advised when combining enzalutamide with drugs that are strong inducers or inhibitors of these CYP450 metabolic pathways. Where possible these drugs should be avoided. In settings where avoidance of these drugs is not possible, suggestions for dose reductions for enzalutamide are described in Section 5.3 and 5.1.2.

Enzalutamide affects the metabolism of some drugs. Clinical data indicate that enzalutamide is a strong inducer of CYP3A4 and a moderate inducer of CYP2C9 and CYP2C19. Concomitant use of enzalutamide with drugs with a narrow therapeutic index that are metabolised by CYP3A4 (e.g. alfentanil, cyclosporine, dihydroergotamine, ergotamine, fentanyl, pimozide, quinidine, sirolimus, tacrolimus), CYP2C9 (e.g. phenytoin, warfarin), and CYP2C19 (e.g. S-mephentoin) should be avoided if possible as enzalutamide may decrease their exposure. If co-administration with warfarin cannot be avoided, additional INR monitoring should be conducted utilising local laboratories.

The 'Use with caution' medication list included in this protocol is not exhaustive. Please refer to the current approved enzalutamide Investigator Brochure.

5.5.4 Prohibited

The following medications should not be used during this study. Participants who require treatment with any of these agents will usually need to discontinue study treatment. This should be discussed with the Study Chair by contacting the NHMRC CTC:

- Other investigational treatments
- Other anti-cancer therapy, including unproven treatments
- Over the counter therapies such as phytoestrogens
- St John's Wort
- Grapefruit juice

5.6 Compliance

Lu-PSMA compliance will be determined by participant attendance for study treatment administration. Enzalutamide compliance will be formally determined by a count of tablets performed at the time of clinic review and out of sight of the participant at Day 15 and Day 43. The participant will be counselled appropriately if significant non-compliance is determined. Compliance at subsequent visits will be assessed at the time of clinic review by questioning the participant, recording if treatment has been taken as prescribed and, if not, the reasons and number of days of treatment missed.

5.7 Study Treatment Discontinuation

Study treatment will be permanently discontinued for any of the following reasons:

- Clinical progressive disease (PD) is documented by a site investigator. PSA progression alone does not constitute clinical progression i.e. if the participant has PSA progression alone they may remain on study drug until the criteria for clinical progression are met.
- Unacceptable toxicity as determined by the participant or site investigator or as defined in section 5.2 or 5.3
- Delay of > 16 weeks from planned day of next Lu-PSMA cycle due to treatment-related adverse events. For delays > 16 weeks due to reasons other than treatment-related adverse events, please contact the study chair or delegate to discuss treatment continuation.
- Delay of enzalutamide > 6 weeks due to treatment-related adverse events. Treatment interruptions and re-initiations should be discussed with the study chair or delegate.

- Multidisciplinary consultation (as a minimum: medical oncology and nuclear medicine physician) determines that continuation of treatment is not in the participant's best interest.
- Occurrence of an exclusion criterion affecting participant safety.
- Required use of a prohibited treatment (section 5.5.4).
- Significant protocol non-compliance, e.g. repeatedly failing to attend scheduled assessments.
- The participant declines further study treatment, or withdraws their consent to participate in the study.
- Evidence that the participant is no longer clinically benefiting.

The reasons for discontinuing treatment will be documented in the participant's medical record and eCRF. Participants who stop study treatment prior to the time recommended in the protocol will be requested to continue follow-up visits according to the protocol.

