12 STUDY TREATMENT SUPPLY AND ACCOUNTABILITY

12.1 *Study Treatment*

The investigational agents are enzalutamide and ^{177}Lu PSMA-617.

PSMA-617 is a small molecule ligand that binds to the extra-cellular domain of the prostate-specific membrane antigen. Each vial is supplied with a chemical purity $\geq 95\%$. Lutetium-177 (^{177}Lu) is a nuclear reactor-produced radiometal with a half-life of 6.7 days. Its decay mode is beta Max 0.5 MeV, average beta 0.13 MeV and gamma 208 keV (11% abundance). It is supplied in the chemical form of Lutetium Chloride (LuCl_3) in 0.04 M HCl with a radionuclide and radiochemical purity of $>99\%$.

No carrier added (n.c.a.) ^{177}Lu and PSMA-617 will be provided as clinical trial stock. The final product ^{177}Lu -PSMA-617 will be compounded on site according to the Nuclear Medicine Manual by a qualified radiopharmacist or radiochemist. Quality control will be performed with HPLC prior to release of product. The study drug will be administered to eligible participants under the supervision of the nuclear medicine investigator or identified co-investigators.

12.2 *Control Treatment*

Enzalutamide is an androgen receptor inhibitor. It is provided as liquid-filled soft gelatine capsules each containing 40 mg enzalutamide for oral administration. Each carton contains 112 capsules. The inactive ingredients are caprylocaproyl polyoxylglycerides, butylated hydroxyanisole, butylated hydroxytoluene, gelatine, sorbitol sorbitan solution, glycerin, purified water, titanium dioxide, and black iron oxide.

Cartons of enzalutamide should be stored below 25°C (77°F) in a dry place.

Full details on product handling information are provided in the Product information, Investigator Brochure and Pharmacy Manual.

12.3 *Drug Accountability*

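### Section 5.7 permanently stops study treatment for drug-specific events without saying which drug stops, and its literal reading does not fit the enzalutamide durations given elsewhere

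*Protocol*

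**What the plan says.** Protocol section 5.7 introduces its list with "Study treatment will be permanently discontinued for any of the following reasons". Some reasons plainly concern everything the participant receives, such as clinical progression or withdrawn consent. Others belong to one drug: "Delay of > 16 weeks from planned day of next Lu-PSMA cycle due to treatment-related adverse events" and "Delay of enzalutamide > 6 weeks due to treatment-related adverse events". The toxicity reason refers to sections 5.2 (Lu-PSMA) and 5.3 (enzalutamide) together. No reason names the drug that is to stop. For long Lu-PSMA delays from other causes there is no automatic stop: "For delays > 16 weeks due to reasons other than treatment-related adverse events, please contact the study chair or delegate to discuss treatment continuation".

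Enzalutamide has its own duration. Section 5.1.2 gives it "orally once daily until clinical disease progression, prohibitive toxicity or participant is no longer clinically benefiting". Table 1 says, for both arms, "Daily until participant is no longer clinically benefiting, or experiences unacceptable toxicity". The synopsis continues it to progression or prohibitive toxicity in both groups. Table 1 gives Lu-PSMA a separate toxicity exit: "All participants receive Lu-PSMA doses 1 and 2 (Days 15 and 57) unless unacceptable toxicity per section 5.2 of protocol".

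**The concern.** A combination-arm man whose Lu-PSMA is held for a long time, but who tolerates enzalutamide and has not progressed, gets one answer from a literal reading of 5.7 and another from Table 1 and 5.1.2. The 16-week rule can be met only in the combination arm, because the control arm has no Lu-PSMA cycles. If sites resolve the wording differently, exposure to the backbone drug in one arm depends on local interpretation. The visit schedule and the safety window follow, because both are tied to the end of study treatment. The aim is to measure the effect of adding Lu-PSMA to enzalutamide, so the protocol should give one answer on whether enzalutamide continues when Lu-PSMA does not.

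**Working it through.** No stated figure is in dispute. The check compares passages and then works out when the rule can take effect.

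**1. What the term covers.**
- Both drugs: the title of Table 1; heading 5.1, which contains 5.1.1 (Lu-PSMA) and 5.1.2 (enzalutamide); the on-treatment column of the 6.1 schedule, which applies to all participants and so must include enzalutamide; and section 12.1, under the heading Study Treatment ("The investigational agents are enzalutamide and" Lu-PSMA-617).
- Lu-PSMA alone: section 5.6, where Lu-PSMA compliance is judged by attendance for study treatment administration; and section 8.3, which speaks of Lu-PSMA study treatment and, separately, of the last enzalutamide dose.

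Usage elsewhere therefore does not settle 5.7.

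**2. One case under each passage.** A combination-arm man has Lu-PSMA held for more than 16 weeks for treatment-related adverse events. He tolerates enzalutamide and has not progressed.

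| Passage | Lu-PSMA | Enzalutamide |
|---|---|---|
| 5.7, literal | stops | stops |
| 5.7, by drug | stops | continues |
| Synopsis, Table 1, 5.1.2 | own rule | continues, unless the Lu-PSMA toxicity itself counts as the toxicity exit |

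The 6-week enzalutamide reason mirrors this: read literally, it also ends Lu-PSMA. That conflict is softer, because section 5.1.1 makes doses 3 and 4 depend on clinical appropriateness and safety criteria.

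**3. When the 16-week limit passes.** Day = planned dosing day + 16 × 7 = planned day + 112; months = day / 30.4375. Dose 2 is the first that toxicity of Lu-PSMA itself can hold.
- Dose 2: 57 + 112 = Day 169, 5.6 months.
- Dose 3: 113 + 112 = Day 225, 7.4 months.
- Dose 4: 169 + 112 = Day 281, 9.2 months.

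These are approximate. Dosing windows are ±7 days, and days count from the start of enzalutamide, which may be up to 7 days after randomisation.

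**4. Against the endpoint.** Section 13.1 assumes a control median PSA PFS of 5 months and a hazard ratio of 0.625. With exponential times the combination median is 5 / 0.625 = 8 months. The share of that arm still free of PSA progression at time t is 0.5^(t/8): 62% at 5.6 months, 53% at 7.4 and 45% at 9.2. Under the plan's own assumptions, then, 38% to 55% of the arm would already have had the primary event. For the rest, a stop could still matter. Men with long toxicity delays may differ from the arm as a whole.

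**5. What changes with the reading.** If study treatment has ended, PSA visits move from 4-weekly to 42 and 84 days after the last dose and then 6-weekly (sections 6.1 and 6.2.1), and adverse-event recording closes 12 weeks later (section 8.2). If enzalutamide continues, neither clock has started. The effects on PSA PFS need not point the same way: losing enzalutamide could bring progression forward, while wider PSA spacing could delay its detection.

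**The case against.** The strongest case on the other side is that 5.7 has a consistent reading. Each delay reason names its drug, the toxicity reason points to one section per drug, and section 8.3 gives the two drugs separate end dates. Read this way, 5.7 agrees with Table 1 and 5.1.2. That reading is available, which is why this is an unreconciled rule and not proof that the protocol intends to withdraw enzalutamide. But 5.7 does not state it, and the same opening sentence governs reasons that clearly end both drugs.

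It can also be said that the toxicity exits in Table 1 and 5.1.2 are not limited to toxicity caused by enzalutamide. That is correct and softens the conflict. It does not remove it, because Table 1 gives Lu-PSMA a separate toxicity exit.

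Three stronger readings are tempting, and the documents do not support them.
- **Bias against the combination.** Follow-up continues after stopping (5.7, 6.4), efficacy is analysed by intention to treat (13.2), the trigger comes late, and the two effects in step 5 can oppose each other.
- **A number of men affected.** The protocol gives no rate for meeting the rule, so any percentage of the combination arm would be invented.
- **A breach of the two-participant allowance in 13.1.** That allowance is for non-adherence to assigned treatment. A man stopped because the protocol requires it is adhering.

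**Conclusion.** The point holds as a gap between a stated rule and the stated treatment durations. Section 5.7 does not say which drug a drug-specific event ends. Its literal reading does not fit the synopsis, Table 1 and 5.1.2, and its drug-by-drug reading does. The possible consequence is inconsistent conduct between sites in the combination arm: in enzalutamide exposure, PSA timing and the adverse-event window. The number affected cannot be derived from the documents. It is probably small, since the rule needs more than 16 weeks of delay attributed to treatment-related adverse events. The randomised comparison stays intact, and the direction of any effect on PSA PFS is uncertain. The timing in steps 3 and 4 rests on the planned dosing days and on exponential PSA PFS with the medians implied by 13.1.

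**What to change.** Reconcile 5.7 with the synopsis, Table 1 and 5.1.2. For each reason in 5.7, state whether it ends Lu-PSMA, enzalutamide or both, including the 16-week and 6-week delays and toxicity under 5.2 or 5.3. State also which stop date starts the post-treatment visits and the adverse-event window when only one drug ends. Which rule applies is a clinical decision for the trial team; the documents need only give one answer.

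Section 5.7 already requires the reasons for discontinuation in the medical record and eCRF. Check that the eCRF, which is not shown, holds stop date and reason separately for each drug, and add them if it does not. The cost is a few words per reason in an amendment and possibly a small eCRF change. No extra participants, visits or procedures are needed.
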